6.7.8. Time to fatal or non-fatal cardiovascular events

Estimand	See Section 5.2.8 for definition
Analysis Set	ITT Population
Methods	Cox proportional hazards model.
Dependent Variable	Time to composite endpoint: fatal or non-fatal cardiovascular events
Cox Model	Fixed effects: 
 • Fixed effects associated with: • Stratifying variables: sUA, HbA1c, study center • Treatment group • Albuminuria status with 2 levels • Baseline AER geometric mean (at Visits 3 and 4 combined) expressed on log base to 10 scale • Baseline iGFR
Results	
 • N(%) of subjects with fatal or non-fatal cardiovascular events during the course of the study • Hazard ratio of allopurinol to placebo • 95% confidence interval for hazard ratio • P-value for treatment effect

6.8. Other analyses

6.8.1. Subgroup analyses

To investigate the possible presence of heterogeneity in the response to allopurinol, subgroup analyses (based on the primary efficacy analysis described in subsection 6.6.1, with the inclusion of appropriate interaction terms with the subgroup variable) will be performed by age groups (≤ 50 and > 50 yrs), gender, racial/ethnic group, HbA1c (≤ 7.8 and $> 7.8\%$), serum uric acid (≤ 6.0 and > 6.0 mg/dl), baseline iGFR (≤ 60 ml/min and > 60 ml/min/1.73m²), AER at baseline (≤ 50 and > 50 mg/24 hr), and albuminuria status (subjects who qualified by ACR or AER or were albuminuric at baseline vs. subjects who did qualify by eGFR slope and were normoalbuminuric at baseline).

An example of such subgroup analysis for age groups (≤ 50 and > 50 yrs) is provided below. Similar to Equation (6.1) for each time t ($t = 1, 2, 3$), corresponding to visits V11, V16, V17, we specify the model:

$$iGFR_{it} = \beta_{0t} + \beta_{1t} TRT_i + \beta_{2t} AGE_i + \beta_{3t} AGE_i \times TRT_i + \mathbf{x}'_i \boldsymbol{\beta} + \epsilon_{it}, \quad (6.2)$$

where $iGFR_{it}$ is the value of iGFR at time t for subject i ($i = 1, \dots, 530$). Fixed effects $\beta_{0t}, \beta_{1t}, \beta_{2t}, \beta_{3t}$ for $t = 1, 2, 3$ denote visit-specific intercepts, treatment effects, age effects and age by treatment interactions, respectively. TRT_i is treatment group (equal to 1 for the allopurinol and 0 for placebo). AGE_i indicates age group (≤ 50 and > 50 yrs). Stratifying variables, and baseline covariates albuminuria status, AER, iGFR for subject i are included in a vector of covariates \mathbf{x}_i and associated fixed effects are stored in vector $\boldsymbol{\beta}$. We assume that residual errors ϵ_{it} ($t = 1, 2, 3$) for subject i are normally distributed with zero mean and 3x3 general/unstructured variance-covariance matrix. The model specified in (6.2) will yield the estimates of visit-specific treatment by age interaction effects $\beta_{31}, \beta_{32}, \beta_{33}$ for all three visits V11, V16 and V17. In the context of subgroup analysis, we are interested in β_{33} , which represents treatment by age interaction at Visit 17 adjusted for baseline covariates.

Analysis	Subgroup Analysis of the Primary Endpoint: iGFR at the end of the 2-month wash-out period (Visit 17) by Age group
Analysis Set	ITT Population
Methods	Linear model for repeated measures with correlated errors
Dependent Variable	iGFR measured at Visits V11 (80 weeks), V16 (156 weeks) and V17 (164 weeks after randomization)
Model	Fixed effects: 
 • Visit-specific intercepts, age effects, treatment effects and age by treatment interaction effects • Stratifying variables: sUA, HbA1c, Study center • Albuminuria status with 2 levels • Baseline AER geometric mean (at Visits 3 and 4 combined) expressed on log base to 10 scale • Baseline iGFR
Results	
 • Estimate of age by treatment interaction at Visit 17 adjusted for baseline covariates • 95% confidence interval for age by treatment effect interaction at Visit 17 • P-value for treatment effect

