11.10. Sample Size

Since a variance-covariance matrix for the iGFR measures is not available and this matrix is essential in order to perform formal power calculations for a model with correlated errors, we performed alternative power calculations based on an intent-to-treat analysis within an ANCOVA framework. Specifically, we assumed that the primary hypothesis is tested in the following model:

$$M1: \text{iGFR at washout} = \text{iGFR at baseline} + \text{treatment group}$$

Compared to the model that will be used in the primary analysis, model M1 is simplified in two aspects. First, it does not use information from iGFR values measured at intermediate time points. Second, it does not include covariates such as the stratifying variables (HbA1c and UA) or other GFR predictors such as baseline AER. Both of these aspects may lead to loss of precision of the treatment effect estimate. Consequently, our sample size calculations should be considered as conservative.

The hypothesis being tested, i.e. the effect of treatment on iGFR at washout, corresponds to testing whether the treatment group factor in Model M1 is significant. The choice of the ANCOVA model for the purpose of power calculations is sensible, as residuals from a univariate model involving baseline iGFR as covariate fitted to data from RASS study conform to normal distribution. Sample size calculations were performed based on Cohen⁴⁵ and making the following assumptions:

1. Postulated effect on iGFR at washout (\cdot) = 3 ml/min/1.73 m². We deem this effect to be clinically meaningful and attainable. It is clinically meaningful because it would translate on average into a 10-year delay in the progression to ESRD. It is attainable because it is smaller than the difference in 3-year GFR that we observed in the JKS between subjects with serum UA \geq 4.5 mg/dl compared to those with levels below this value. The postulated effect was based on the following changes in GFR levels in the two treatment groups:

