 - a. Untreated group = 3 ml/min/1.73 m² per year. This estimate is based on data from the Joslin Kidney Study (JKS), in which the median GFR loss among 43 subjects meeting the above criteria was 3.1 ml/min/1.73 m² per year, with 70% of subjects having a GFR loss $>$ 1.5 ml/min/1.73 m² per year. Also, among 116 subjects from Steno who met the albuminuria and GFR criteria, but for whom serum uric acid values were not available, the median GFR loss was 3.3 ml/min/1.73 m² per year, with 71% of subjects having a GFR loss $>$ 1.5 ml/min/1.73 m² per year.
 - b. Treated group = 2 ml/min/1.73 m² per year. The average GFR loss in the JKS subjects with serum UA $<$ 4.5 mg/dl was 1.5 ml/min per year. On this basis, we conservatively assumed that the allopurinol treatment, if effective, would decrease the GFR loss to 2 ml/min per year (a 33% decrease compared to the untreated group).

2. Standard deviation (SD) of residual error = 10.1 ml/min/1.73 m². This was estimated based on the root-mean-squared error from a regression model with eGFR at 3 yrs as the dependent variable and baseline eGFR as the independent variable fitted to data concerning T1D patients from the Joslin Kidney Study meeting the PERL inclusion criteria.

Assuming a two-sided alpha error equal to 0.05, the effective sample size needed to detect the pre-specified treatment effect ($\delta = 3$ ml/min/1.73 m²) at washout adjusted for baseline iGFR with 80% power is equal to n=180 per group. To take into account the anticipated overall dropout rate (up to 5%/yr or 15% over the entire duration of the study) and drug discontinuation or non-compliance in the treatment group (up to 2%/yr or 6% over the entire duration of the study), and to maintain the desired

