power of at least 80%, it will be necessary to recruit n=240 subjects per group. In Table 1, we show the power of the proposed sample size for Model M1 under different dropout and non-compliance scenarios. We also provide the corresponding power for a model (Model M2) including the two stratifying variables (Hb1Ac and UA) and baseline AER as covariates to illustrate the effect of adding these variables to Model M1. In this analysis, we assumed that adding these covariates reduces the residual variance by 10%, which corresponds to these covariates explaining merely 4% of the total iGFR variation over and above the variability explained by iGFR at baseline. As shown in Table 1, once these covariates are accounted for, power is expected to exceed the conservative estimates provided by Model M1 and reach almost 90% for 15% dropout and 6% non-compliance rates.

Table 1. Power to detect treatment effect for two ANCOVA models under different drop-out and non-compliance scenarios.

Overall Dropout (%)	Non-compliance (%)	Model	
		M1	M2
9	0	.87	.92
12	0	.86	.91
15	0	.85	.90
9	6	.83	.89
12	6	.82	.88
15	6	.80	.87

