6.7.2. iGFR time trajectory estimated from repeated iGFR measurements	19
6.7.3. eGFR at 4 months after randomization (Visit 7).....	20
6.7.4. eGFR time trajectory	20
6.7.5. Time to serum creatinine doubling or ESRD	21
6.7.6. Urinary AER at the end of the wash-out period.....	21
6.7.7. Urinary AER during the last three months of the treatment period (Visits 15 and 16).	22
6.7.8. Time to fatal or non-fatal cardiovascular events	22
6.8. Other analyses	23
6.8.1. Subgroup analyses.....	23
6.8.2. Analyses of safety outcomes	24
6.8.3 Analyses of other measures	24
6.8.4. Analysis of the effect of post-randomization sUA changes on iGFR value at Visit 17	25
6.8.5. Time to 40% eGFR decrease.....	26
6.8.6. Time to doubling of serum creatinine, end-stage renal disease (ESRD), or cardiovascular/renal death.....	26
6.9. Model assumptions and alternative analyses	27
ACKNOWLEDGEMENTS.....	28
REFERENCES	29
APPENDIX I. Study Objective, Study Design, Outcomes & Statistical Analysis and Data Management Sections from Protocol.....	30

1. Overview

DESIGN:

- Multicenter, double-blind, placebo-controlled, parallel-group randomized clinical trial.
- N=530 total number of subjects

STUDY POPULATION:

- Type 1 Diabetes
- Inclusion/Exclusion Criteria listed in the Study Protocol

STUDY TREATMENTS:

- Oral allopurinol or placebo administered for 3 years followed by a 2-month drug washout

PRIMARY OUTCOME MEASURE:

[figure not shown]
- iGFR at the end of the 2-month wash-out period following the 3-year intervention

STATISTICAL ANALYSIS PLAN:

- This plan will be finalized prior to the database lock and unblinding of treatment groups

2. Schema

Figure 2.1. PERL Study Schema

3. Rationale for Adjustments of Statistical Analysis Plan as Compared to Protocol (Version 10, approved by DSMB on March 6, 2018)

Changes from the protocol-specified definitions of aims, outcomes, and statistical analytical approaches are outlined below. These changes reflect internal discussions since the initiation of the study that have not been incorporated as protocol amendments, but were discussed during the preparation of the Statistical Analysis Plan. These changes and the rationale for their implementation are documented herein and represent changes made prior to the database lock and unblinding of the study.

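### SAP 6.8.1 lists a p-value for the treatment effect beside the interaction estimate and its confidence interval; the p-value should be the one for the interaction

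*SAP*

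**What the plan says.** SAP 6.8.1 introduces the subgroup analyses as a search for heterogeneity in the response to allopurinol across eight variables: age, gender, racial/ethnic group, HbA1c, serum uric acid, baseline iGFR, baseline AER and albuminuria status. Age is worked through as the example. Equation 6.2 has four visit-specific terms, and the text labels them separately: intercepts (β₀ₜ), treatment effects (β₁ₜ), age effects (β₂ₜ) and age-by-treatment interactions (β₃ₜ). The text then says that interest lies in β₃₃, "which represents treatment by age interaction at Visit 17 adjusted for baseline covariates".

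The results row of the table that follows has three entries: the estimate of the age-by-treatment interaction at Visit 17, the 95% CI for that interaction, and "P-value for treatment effect". Neither document lists a p-value for an interaction.

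Treatment is coded 1 for allopurinol and 0 for placebo. Age is said only to indicate the age group; neither the coding nor the reference level is given. Protocol 11.7, reproduced in SAP Appendix I, calls the subgroup analyses strictly exploratory.

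**The concern.** The first two entries of the row concern β₃₃. The third, by the SAP's own naming of the terms in equation 6.2, concerns β₁ₜ. The row therefore attaches to an interaction estimate a p-value for a different hypothesis.

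The wording does not look like deliberate shorthand. The same line closes the main-effect tables (for example SAP 6.6.1 and 6.7.8), where it is right. In SAP 6.8.4, where the target is the effect of uric acid change, the p-value line was rewritten to match. The subgroup row was not, and the February 2017 SAP (its Section 6.7) has the same line. The table shells were dropped from the 2019 SAP, so this row is the only output specification left for these analyses.

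At stake is the reading of the subgroup results. A p-value that responds to whether the drug works says nothing about whether it works differently in different patients.

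**Working it through.** **Inputs from Protocol 11.10 and SAP Section 1**
- Test level: "Assuming a two-sided alpha error equal to 0.05".
- Effect at washout: "3 ml/min/1.73 m². We deem this effect to be clinically meaningful and attainable".
- Residual spread: "Standard deviation (SD) of residual error = 10.1 ml/min/1.73 m²".
- Planned recruitment: "it will be necessary to recruit n=240 subjects per group".
- Size given in the SAP: "N=530 total number of subjects", so 265 per arm at 1:1.
- Dropout up to 15%; non-compliance in the treated arm up to 6%.

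**Assumptions not in the documents**
- Age coded 0/1.
- Share f of participants in the reference age group between 40% and 60%. SAP 3.3 gives a cut at 50 and a median age of 52 but no share, and either group could be the reference.
- Visit 17 treated as a single ANCOVA, without the earlier visits or the imputation.

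**Reproducing the plan's own figures.** n per arm = 2(1.960 + 0.842)² × 10.1² / 3² = 178 by the normal approximation, or 179 using the t distribution. The protocol states "with 80% power is equal to n=180 per group", which agrees. For Table 1, Model M1, 15% dropout leaves 240 × 0.85 = 204 per arm, so SE = 10.1 × √(2/204) = 1.00. Power is Φ(3/1.00 − 1.96) = 0.85 with full compliance and Φ(2.82/1.00 − 1.96) = 0.805 with 6% non-compliance (3 × 0.94 = 2.82). The stated values are .85 and .80.

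**The listed p-value under a uniform effect.** Evaluable participants per arm: 265 × 0.85 = 225.25. Under 0/1 coding β₁₃ is the effect in the reference group, with SE = 10.1 × √(2 / (225.25 f)). The chance of p < 0.05 is Φ(δ/SE − 1.96) plus a negligible lower tail.

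| f | n per arm in reference group | SE | 3/SE | p < 0.05, δ = 3 | p < 0.05, δ = 2.82 |
|---|---|---|---|---|---|
| 0.40 | 90.1 | 1.505 | 1.99 | 51% | 47% |
| 0.45 | 101.4 | 1.419 | 2.11 | 56% | 51% |
| 0.50 | 112.6 | 1.346 | 2.23 | 61% | 55% |
| 0.55 | 123.9 | 1.283 | 2.34 | 65% | 59% |
| 0.60 | 135.2 | 1.229 | 2.44 | 69% | 63% |

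With the protocol's 480 participants, 15% dropout and 6% non-compliance, the range is 43–59%. A uniform effect is not heterogeneity, so the interaction test would reject in 5% of trials.

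**Dependence on the true effect** (f = 0.45 to 0.55, full compliance): 29–34% at 2 ml/min, 11–12% at 1 ml/min, 5% at zero.

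**Centred coding.** β₁₃ becomes roughly the average effect, with SE = 10.1 × √(2/225.25) = 0.952 and 3/0.952 = 3.15, giving p < 0.05 in 88% of trials.

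**Simulation** (20,000 trials, 450 evaluable, f = 0.45, uniform effect 3): β₁₃ was significant in 56.2% and β₃₃ in 4.7%. In 53.9% of trials a p-value below 0.05 for β₁₃ would stand beside an interaction CI that includes zero.

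**The case against.** The intended analysis is clear. The text names β₃₃, Protocol 11.7 asks for a treatment-by-subgroup interaction term, and the interaction CI is listed. The CI line contains the words treatment effect as part of its name for the interaction, so the last line may be a clipped version of it. A programmer who follows the text would produce the right p-value. A reader who looks at the CI would see whether the interaction is significant at 5%. All of this stands. It makes this an error in the output list, not a wrong choice of analysis.

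Three stronger readings are tempting and go beyond the documents.
- A reader might infer that a uniform drug effect would routinely be reported as heterogeneity. That needs the label to be programmed literally, the adjacent CI to be ignored, and a real drug effect of about the design size.
- A reader might state as fact that the p-value tests the effect in one subgroup. That holds under 0/1 coding, which the SAP does not specify.
- A reader might add that a benefit confined to the non-reference group would be missed. With an effect of 6 in that group and 0 in the reference group, the interaction test has about 88% power and a 0/1-coded β₁₃ only 5%. This again depends on the coding: under centred coding with equal halves, β₁₃ would be about 3. An effect of 6 is also twice the design value and is not in the plan.

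What the objection does not remove is that, under either coding, the listed p-value is not a test of heterogeneity, and no interaction p-value is listed.

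**Conclusion.** The results row in SAP 6.8.1 specifies the wrong p-value for an analysis of heterogeneity. The size of the problem is conditional. With the line programmed literally, 0/1 coding, a 40–60% reference share and a uniform true effect of 3 ml/min/1.73 m², a nominally significant result would appear in about half to two-thirds of trials although no interaction exists. The excess over 5% shrinks with the true effect and vanishes if the drug does nothing. Severity is low: the intended parameter is named, the correct interval stands beside the p-value, the analyses are exploratory, and nothing in the primary analysis depends on this line.

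**What to change.** Replace the last entry of the results row with: *P-value for the age-by-treatment interaction at Visit 17 (test of β₃₃ = 0)*. Say that the corresponding interaction p-value applies to each of the other subgroup variables. For any variable with more than two levels, such as racial/ethnic group if it is kept in several categories, specify a joint test of all its interaction terms at Visit 17.

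The cost is a line or two of SAP wording. The fitted model already yields the quantity, and no new data or model is needed. Reporting the Visit 17 effect within each level would be a presentation choice; its absence is not an error.

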6.8.2. Analyses of safety outcomes

Safety measures are assessed during three periods of the study: run-in (Visits 1-5), on-treatment (after Visit 5 through Visit 16), and off-treatment washout (after Visit 16 through Visit 17). Safety will be summarized overall (treatment and off-treatment combined) and by period, depending on the safety outcome of interest during that period.

- Percentage of subjects with and number of SAEs, time to first SAEs during on-treatment period and overall by MedDRA System Organ Class and by MedDRA Preferred Term Categories.
- Percentage of subjects with and number of permanent discontinuations of study medication because of adverse effects on-treatment period and overall.
- Percentage of subjects with and number of AEs, overall and by severity and by relatedness to study medication during on-treatment period and overall.
- Percentage and number of subjects with skin rash during on-treatment period and overall.

For dichotomous safety outcomes, the proportion of subjects experiencing adverse outcomes (AEs, SAEs) will be summarized by treatment group and compared by means of odds ratios and 95% CIs. Poisson regression models will be used for safety outcomes (e.g., SAEs and AEs) with multiple recurrences per patient, with the logarithm of the period of observation from the time of study medication used as the offset. Time to first SAE will be analyzed using Kaplan-Meier methods to estimate the SAE-free distributions for each treatment group. This analysis will employ the ITT analysis set. No imputation for missing data will be used.

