5.5.2. Handling of study drug discontinuation

- Date and reason for drug discontinuation will be recorded on the relevant Case Report Form.
- All study discontinuations decided by a clinical site will have to be reviewed and approved by the Drug Monitoring Committee within 10 days from their start.
- If the study drug is discontinued due to treatment with medications that make allopurinol contraindicated (e.g. amoxicillin/ampicillin) or due to pregnancy/breastfeeding, the possibility of resuming the study drug will be evaluated by the Drug Monitoring Committee once those medications have been discontinued or pregnancy/breastfeeding has ended.

- If the study drug is temporarily discontinued and then re-instated, the end-date of the intervention will remain the same as if the study drug had not been discontinued. All visits will be carried out as scheduled while the study drug is temporarily discontinued.
- Unless a participant withdraws consent all participants that are permanently discontinued from study drug or who discontinue study medication on their own will be followed for the full study period (i.e., 164 weeks, including the washout period) and all data will be collected as scheduled.
- If a participant reaches ESRD as defined above under 5.5.1,, he/she will be permanently discontinued from the study and invited to participate in a study close-out call or visit to be held within three months from the occurrence of ESRD. Data collection at this call or visit will be limited to standard adverse event reporting. In addition, sites should continue to contact participants who have reached end-stage renal disease to determine their final status until 3 years and 2 months after randomization. Major attempts will be made to schedule an end-of-study assessment for all participants who are lost to follow-up during the course of the study.

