8.6. End of Intervention (Visit 16)

At the end of the treatment period (Visit 16), the following procedures will be completed for each participant:

- Obtain interval medical history (with special emphasis on CVD events).
- Review of concomitant medications and AEs.
- Review RASB and BP therapy.
- Collect unused study medication and document compliance.

- Measure height, weight and vital signs.
- Inspect for skin rash.
- Conduct a physical exam.
- Perform ECG.
- Collect samples for clinical laboratory assessments as outlined in Figure 1 and for storage for later biomarker research.
- Perform pregnancy test in women of childbearing potential.
- Measure iGFR.
- Provide containers and instructions for 2 overnight urine collections to be made immediately before Visit 17.

Participants will be instructed to stop taking the study medication and to mail the pill bottles or the blister packs with the tablets remaining from the last prescription to the study center if they did not already bring the unused study medication at the visit. The RAS and BP therapy will be continued as before until the closing visit (Visit 17). The importance of coming back in 8 weeks for the closing visit (Visit 17) will be emphasized.

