10. ADVERSE EVENT REPORTING

10.1. Definitions

An Adverse Event (AE) is any untoward medical occurrence in a study participant regardless of its relationship to study treatment. A treatment-emergent AE is an adverse event occurring during the period between the first dose and 30 days after the final dose of the study medication. A Serious Adverse Event (SAE) is any untoward medical occurrence that results in death, is life-threatening, requires hospitalization or prolongation of an existing hospitalization, results in persistent or significant disability, or is a congenital anomaly/birth defect. Important medical events that do not fall into the above categories may also be considered an SAE when, based on medical judgment, such events may jeopardize the patient's safety and require medical/surgical intervention to prevent one of the outcomes listed in the SAE definition. The term SAE is not intended as a measure of severity or intensity. All AE's/SAE's that occur after the time of informed consent will be reported.

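### SAP 6.8.2 labels all time from Visit 5 to Visit 16 on-treatment whatever the drug status, and does not use the protocol's own treatment-emergent window

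*SAP*

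**What the plan says.** SAP 6.8.2 names the two post-randomization safety periods by visit alone: "on-treatment (after Visit 5 through Visit 16), and off-treatment washout (after Visit 16 through Visit 17". SAEs, AEs, discontinuations for adverse effects and skin rash are each summarised for the on-treatment period and also overall, where overall pools both periods. Recurrent events go into Poisson models with the "logarithm of the period of observation from the time of study medication used as the offset". Time to first SAE is estimated by Kaplan-Meier, with no censoring rule given. The analysis set is ITT.

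Protocol 10.1, reprinted in the SAP appendix, works from dosing instead: "A treatment-emergent AE is an adverse event occurring during the period between the first dose and 30 days after the final dose" of study medication. Neither SAP 6.8.2 nor Protocol 11.8 uses that term, and SAP section 3, which lists departures from the protocol, does not mention dropping it.

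Under Protocol 5.5.2, a participant who stops drug permanently without withdrawing consent "will be followed for the full study period (i.e., 164 weeks, including the washout period) and all data will be collected as scheduled". For temporary stops, "All visits will be carried out as scheduled while the study drug is temporarily discontinued". The same section says "Date and reason for drug discontinuation will be recorded on the relevant Case Report Form". At Visit 16, under Protocol 8.6, "Participants will be instructed to stop taking the study medication", and the washout that follows lasts 8 weeks (Protocol 8.7).

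**The concern.** A reader will take an on-treatment safety table to describe people taking the drug. As defined, it does not. Someone who stops permanently in the first weeks stays in the table, with events and person-time, until Visit 16. Someone who takes drug to Visit 16 leaves it on that day, although the protocol treats the next 30 days as treatment-emergent.

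If a drug-related excess fades once the drug is stopped, off-drug time in the on-treatment rates pulls the rate ratio toward 1, the unhelpful direction for a safety comparison. Events soon after the last dose at Visit 16 are also left out of the on-treatment results. The plan therefore holds two definitions of the drug period that have not been reconciled.

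**Working it through.** SAP 6.8.2 states no numerical result to reproduce. The only discontinuation rate is in Protocol 11.10: up to 6% over the study for drug discontinuation or non-compliance in the treatment group. That section's arithmetic holds. Effect 3, SD 10.1, 80% power and two-sided 0.05 give 178 per arm against the stated 180. At 15% dropout and 6% non-compliance (204 per arm, effect 2.82), power is 0.805 against the stated .80.

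**Inputs.** Visit 16 is week 156 and Visit 17 is week 164 (Protocol, Figure 1). N is 530 (SAP section 1), taken as 265 per arm under 1:1 allocation. Assumptions: permanent stopping times uniform over 156 weeks, full follow-up, a constant background event rate and an off-drug rate ratio of 1.

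**One participant, early stop.** Off-drug weeks labelled on-treatment = 156 − stop week. A stop at week 4, 26, 52 or 104 gives 152, 130, 104 or 52 weeks. Beyond the 30-day tail (4.3 weeks), these are about 148, 126, 100 and 48 weeks.

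**One participant, dosed to Visit 16.** The washout is 164 − 156 = 8 weeks = 56 days, and 30/56 = 54% of it is treatment-emergent under Protocol 10.1. The share is 71% if Visit 17 falls at 6 weeks, 36% at 12 weeks and 21% at the 20-week analysis limit in SAP Table 6.3.2. Against the 156 × 7 = 1,092 days of the on-treatment period, 30 days is 2.7%.

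**Allopurinol arm.** Total person-time is 265 × 1,092 / 365.25 = 792 person-years. Off-drug share = fraction stopping × 0.5. Diluted rate ratio = 2.0 × (1 − share) + 1 × share.

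| Fraction stopping | Off-drug person-years | Share | Rate ratio 2.0 reads as |
|---|---|---|---|
| 6% (planned) | 23.8 | 3.0% | 1.97 |
| 10% (assumed) | 39.6 | 5% | 1.95 |
| 20% (assumed) | 79.2 | 10% | 1.90 |
| 30% (assumed) | 118.8 | 15% | 1.85 |

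**What the Protocol 10.1 window would change at 6%.** It removes about 22.5 off-drug person-years (time more than 30 days after an early stop) and adds about 265 × 0.94 × 30 / 365.25 = 20.5 person-years of tail after Visit 16. Off-drug time becomes 23.8 − 22.5 + 20.5 = 21.8 of about 790 person-years, or 2.8%, and 2.0 still reads as 1.97. At an assumed 20%, the same window gives about 1.97 instead of 1.90.

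**The case against.** The strongest defence is that this is a legitimate ITT safety summary by assigned arm and scheduled period, and that no stated analysis is contradicted, because neither SAP 6.8.2 nor Protocol 11.8 promises treatment-emergent tables. Cutting follow-up at drug stop can bring informative censoring. The half-lives in Protocol 6.1.1 (about 1-2 hours for allopurinol, 15 hours for oxypurinol) also make the planned stop a defensible end point. This stands as a reason to keep the scheduled-period table. It does not justify calling that table on-treatment, or leaving a protocol-defined window unused without saying so.

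Four stronger readings are tempting, and the documents do not support them.

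- *Late reactions are hidden.* They are not: every listed outcome is also summarised overall, so an event in the 30 days after the last dose is still reported by arm.
- *The dilution is material.* That needs a stopping rate well above 6%, and no passage gives one. Even the 6% includes non-compliance, which a first-to-last-dose window does not remove. It does not remove temporary interruptions either, and participants reaching ESRD leave scheduled follow-up and add little.
- *The dilution is concentrated in people who stopped because of a reaction.* Protocol 5.5.1, 5.5.2 and 9.5 list many other reasons, including contraindicated medication, pregnancy, gout, renal decline and personal choice. Someone who stopped for a rash already counts in the rash proportion, and later off-drug weeks cannot undo that. The person-time arithmetic bears on the Poisson models, not on the odds ratios.
- *The offset is specified to run past discontinuation.* The wording gives a start and no end, so it is ambiguous. It does not limit time to drug exposure, but it is not an explicit rule either way.

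**Conclusion.** The mismatch is established from the text. The visit-based period counts off-drug follow-up as on-treatment and places up to 30 treatment-emergent days per full-course participant in the washout. No events are lost.

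The numerical effect is small at the only rate the documents give: about 3% of allopurinol-arm person-time, or 0.03 on a rate ratio of 2.0, under uniform stopping and no off-drug effect. At that rate the protocol window leaves the aggregate rate ratio essentially unchanged. The case for acting therefore rests on a label that is wrong as written and on a protocol definition that no analysis uses. Protection against higher stopping rates is a further benefit, but its size is an assumption.

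The start has the same looseness. Protocol 8.4 mails the drug after randomization, so the period opens before the first dose. The February 2017 SAP (section 3.1) records that some randomized participants took none, and for them an offset counted from study medication has no origin. This is worth correcting because it is cheap, not because it threatens the safety conclusions.

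**What to change.** In SAP 6.8.2:

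1. Add a treatment-emergent analysis of AEs, SAEs and skin rash on the Protocol 10.1 window, from first dose to 30 days after the final dose, using dosing records and the discontinuation dates on the CRF, among participants who took at least one dose.
2. For that analysis, end the Poisson offset and the time-to-first-SAE censoring at the same date.
3. Relabel the existing period 'Visit 5 to Visit 16 regardless of drug status', and keep it and the overall table as the ITT summaries.

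The cost is one derived date per participant and one extra set of tables. The derivation is feasible: the February 2017 SAP shell for time to first SAE already censored at the end of study medication. The drawback is possible informative censoring at drug stop, which the retained ITT summaries offset.
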